#### 8.3.3 All participants (Cohort 1A, Cohort 1B, Cohort 2)

In the safety and efficacy study the clinical and functional assessments will be done at 6 months and 7 years; and at 1, 2, 3, 5 and 10 years assessment of the clinical, functional and radiographic performance.

An interim analysis describing the safety and efficacy parameters is planned at 6 months and annually, and a final analysis will be done at 10 years. The interim analysis will consider the overall study population as well as the following pre-defined subgroups:

- Female Resurfacing Patients
- Patients implanted with a small femoral head diameter (Size 46 and below)
- Patients operated on pre- and post- the design upgrade

The interim analyses shall be independently reviewed by the Karolinska Institute in Stockholm, Sweden up to the 2 year interval.

## 8.3.4 Analysis reporting time-points

## Table 1 Reporting time-points

Report Title	Time point	Cohort(s)	Independent Review?	Data	
Gateway Safety Analysis 1	2 days	1A	Yes	Complication rate, Radiological Assessment	
Safety Evaluation 6 weeks	6 weeks	1A	Yes	Complication rate, Functional Outcomes, Radiological Assessment	
Safety Evaluation 3 months	3 months	1A	Yes	Complication rate, Functional Outcomes, CT Assessment, Toxicology	
Safety Evaluation 6 months	6 months	1A	Yes	Complication rate, Functional Outcomes, CT Assessment, Toxicology	
Gateway Safety Analysis 2	6 months	1B	Yes	Complication rate, Functional Outcomes, CT Assessment, Toxicology	
Interim Analysis 6 months	6 months	1A,1B,2	Yes	Complication rate, Functional Outcomes, CT Assessment (Cohort 1A and 1B only), Toxicology (Cohort 1A only), PROMS, Survivorship	
Safety Evaluation 1 year	1 year	1B	Yes	Complication rate, Functional Outcomes, CT Assessment, Toxicology	
Interim Analysis 1 year	1 year	1A,2	Yes	Complication rate, Radiological Assessment, Functional Outcomes, CT Assessment (Cohort 1A and 1B only), Toxicology (Cohort 1A only), PROMS, Survivorship	
Interim Analysis 2 years	2 years	1A,1B,2	Yes	Complication rate, Radiological Assessment, Functional Outcomes, CT Assessment (Cohort 1A and 1B only), Toxicology (Cohort 1A only), PROMS, Survivorship	
Interim Analysis 3 years	3 years	1A,1B,2	No	Complication rate, Radiological Assessment, Functional Outcomes, PROMS, Survivorship	
Interim Analysis 4 years	4 years	1A,1B	No	Complication rate, PROMS, Survivorship	
Interim Analysis 5 years	5 years	1A,1B,2	No	Complication rate, Radiological Assessment, Functional Outcomes, PROMS, Survivorship	
Interim Analysis 6 years	6 years	1A,1B	No	Complication rate, PROMS, Survivorship	
Interim Analysis 7 years	7 years	1A,1B,2	No	Complication rate, Functional Outcomes, PROMS, Survivorship	
Interim Analysis 8 years	8 years	1A,1B	No	Complication rate, PROMS, Survivorship	
Interim Analysis 9 years	9 years	1A,1B	No	Complication rate, PROMS, Survivorship	
Final Analysis 10 years	10 years	1A,1B,2	No	Complication rate, Radiological Assessment, Functional Outcomes, PROMS, Survivorship	

# 9 Investigation Population

# 9.1 Indications for H1 hip resurfacing arthroplasty

Indications for use of the H1 HRA in this investigation will be patients with end-stage hip disease who are candidates for primary hip arthroplasty using either a metal-on-metal hip resurfacing or a ceramic-on-ceramic THR. Typically they will be younger (<70 years) and active males and females with end-stage hip osteoarthritis, avascular necrosis of the femoral head, post-traumatic osteoarthritis or developmental dysplasia of the hip (DDH). Patients recruited in cohort 2 that require a bilateral HRA will be able to undergo simultaneous bilateral hip resurfacing with the H1 implant.

# 9.2 Bilateral H1 Hip Resurfacing patients

#### 9.2.1 Simultaneous Bilateral HRA (Cohort 2 only)

Patients who require a simultaneous bilateral hip resurfacing with the H1 implant will undergo all assessments as detailed in Table 5. These patients will undergo additional Lateral radiographs and will be required to complete the following questionnaires for the contralateral hip: Oxford Hip Score, EQ5D-5L, Harris Hip Score and Imperial Score (online only).

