#### Patient Reported Outcome Measures and objective clinical and functional outcomes

Data that will be collected as part of the clinical follow-up will include x-rays and subjective hip and general health clinical evaluation including PROMs (Harris Hip Score (HHS) and the Oxford Hip Score (OHS) [39]). The patients' opinion about their state of health, according to a visual analogue scale and 5 dimensions - mobility, self-care, usual activities, pain/discomfort and anxiety/depression, (each dimension having 5 levels: no problems, slight problems, moderate problems, severe problems and extremely) - will be assessed with the EQ-5D questionnaire [40]. Patient satisfaction, expectations and a self-assessment of the physical outcome will also be done according to the new Imperial Score evaluating pain, function and fulfilment of preoperative aspirations after hip arthroplasty. The Imperial Score can only be collected online.

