#### 9.2.2 Staggered Bilateral HRA

Patients who are enrolled into the study as part of Cohort 1A, Cohort 1B or 2 can undergo a HRA with a H1 implant on the contralateral side if they meet the inclusion/exclusion criteria, and pass the screening assessments. All staggered bilateral patients recruitment must be re-consented for the additional assessments before taking part in the study for their contralateral hip. At point of re-consent these patients will be registered again with the coordinating site for a unique identification number for their contralateral second hip.

Patients recruited in cohort 1A who opt to undergo HRA for the contralateral hip will follow the assessments as detailed in Table 6. Those patients in cohort 2 who opt to

undergo HRA for the contralateral hip will follow assessments as detailed in Table 7. Patients recruited in cohort 1B will follow the assessments as detailed in Table 8. These patients will undergo additional AP and Lateral radiographs and will be required to complete the following questionnaires for the contralateral second hip: Oxford Hip Score, EQ5D-5L, Harris Hip Score and Imperial Score (online only).

Bilateral and staggered bilateral patients can be recruited from all sites participating in the trial, however the total number of bilateral implants cannot exceed 20% of the total study sample size (250). Therefore only 25 patients (50 hips) can be recruited as a bilateral or staggered bilateral patient, once this number has been reached, recruitment for the contralateral hip will cease and recruitment will continue for uni-lateral hips only. Bilateral patients and those recruited for the contralateral hip as staggered bilateral patients will be registered as a separate patient for each hip with a unique trial identification number for both hips. Case Report Forms will be completed for each hip.

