# Table 5. Schedule of procedures: Cohort 2 simultaneous bilateral patients – All sites (except \* which are UK sites only and \*\* which are online only)

		_						Post-op				
	Date	Pre-op	Op day	2 days	6 weeks	6 months	1 year	2 years	3 years	5 years	7 years	10 years
	Deviation window	≤4 mos prior	0	±1 day	±2 weeks	±2 weeks	±2 weeks	±4 weeks	±4weeks	±3 months	±3 months	±3 months
	Informed consent	✓										
	Inclusions/exclusions	√ √										
	Patient registration	√√										
	DXA Scan	✓ ≤12 mos prior										
	Medical history	√ √										
	Operative data		$\checkmark\checkmark$									
	Treadmill gait*	√*					√*			√*		
ient	Harris Hip Score	√ √			√√	√ √	√ √	√√	√√	√√	√ √	√√
Assessment	Oxford Hip score	√ √			$\checkmark\checkmark$	√ √	$\checkmark\checkmark$	√ √	$\checkmark\checkmark$	√ √	$\checkmark\checkmark$	$\checkmark\checkmark$
Asse	Imperial Hip Score**	√√**			√√**	√	√√ **	√√**	√√**	√√ **	√√ **	√√**
	EQ-5D	√ √			~~	√ √	√√	~~	√ √	~~	√ √	√ √
	AP Radiographs	✓ ≤12 mos prior		✓	✓		~	~	~	~		✓
	Lateral Radiographs	

✓✓ ≤12

mos prior

		~~	~~		√ √	~~	√ √	~~		√ √
	Low dose CT scan*	<pre>✓*^ ≤12 mos prior</pre>										
	Conmed questions	√ √	√ √	~ ~	~~	√ √	√√	~~	√ √	~~	√√	√ √
	Record Adverse Event(s)	vv	~ ~	~~	√ √	√ √	√ √	√ √	√√	√ √	√√	√√

 $\sqrt{4}$  = Separate assessments to be taken for both hips

### Table 6. Schedule of procedures: Staggered bilateral patient recruited from Cohort 1A into Cohort 2

	t Study Hip hort 1A)	Pre-op	Op day	2D	6 wks	3 mos	6 mos					1 year			2 years		3 years		4 years	5 years		6 years	7 years		8,9 years	10 years	
	tralateral Second dy Hip (Cohort 2)							Pre-op	OP Day	2 D	6 wks		6 mos	1 year		2 years		3 years			5 years			7 years			10 years
	Re-consent for contralateral Hip				1	1		 																			
	Inclusion/exclusion							 																			
	Patient registration							 																			
	DXA Scan							√^ ≤12 mos prior																			
	Medical History							 																			
	Operative data								 																		
ţ	Treadmill gait							 				✓		 						✓	 						

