## 11.4 Objective Outcome Measures

A Harris Hip Score (HHS) will be completed at all postoperative visits.

A gait analysis on a treadmill (MSk Lab, Michael Uren Hub) will be performed in all UK patients who have given permission as per study consent form, pre-operatively and postoperatively at 1 and 5 years. The gait analysis will take place at the MSk Lab using an instrumented treadmill (h/p/cosmos Gaitway II S), equipped with 2 calibrated force plates. The gait parameters will be assessed for each side (prosthetic and non-operated), at a treadmill speed starting from 3/4kph and then at increasing 0.5kph increments to the maximum walking speed of the patient and will include walking on a flat surface and walking on an incline. Leg length measurements will be taken. Patient will be free to terminate the session at any time.

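### Bilateral patients are asked for a separate EQ-5D for each hip, although the protocol describes it as a measure of the whole person's health

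*Protocol*

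**What the plan says.** **EQ-5D.** Section 8.2.1 of the protocol presents the EQ-5D as "The patients' opinion about their state of health, according to a visual analogue scale and 5 dimensions". The dimensions include self-care and anxiety/depression, and nothing in the description refers to one hip.

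The bilateral sections treat it as a hip measure:
- Section 9.2.1 (simultaneous, Cohort 2 only): patients "complete the following questionnaires for the contralateral hip: Oxford Hip Score, EQ5D-5L, Harris Hip Score and Imperial Score (online only".
- Section 9.2.2 (staggered): patients "complete the following questionnaires for the contralateral second hip: Oxford Hip Score, EQ5D-5L, Harris Hip Score and Imperial Score (online only".
- Table 5 puts a double tick on the EQ-5D at every visit where it is due. The key reads "Separate assessments to be taken for both hips".
- Tables 6 to 9 schedule it for each study hip of staggered patients.
- Section 9.2.2 adds that bilateral patients "will be registered as a separate patient for each hip with a unique trial identification number for both hips" and that "Case Report Forms will be completed for each hip".

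Section 9.2.2 caps bilateral recruitment at 20% of 250, given as 25 patients or 50 hips.

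**Gait.** Section 11.4 says: "The gait parameters will be assessed for each side (prosthetic and non-operated". Gait is tested in consenting UK patients before surgery and at 1 and 5 years. Table 5 keeps it for simultaneous bilateral patients at UK sites, with a single tick.

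**The concern.** A simultaneous bilateral patient has to answer general-health questions twice at one visit, and the answers are filed as if from two patients. Section 10.2 plans 95% confidence intervals for averages, and Table 1 puts the patient-reported outcomes in every interim analysis and the final one. Section 7.1.2 sets a non-inferiority goal for these outcomes at each follow-up visit. If hip records are averaged as they are filed, bilateral patients count double and the interval is too narrow.

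In staggered patients the difficulty is timing. A general-health answer filed as the first hip's 1-year result, but given soon after surgery on the other hip, does not describe health one year after a single operation.

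On gait, a simultaneous bilateral patient has no non-operated side after surgery, and a staggered patient has none after the second operation. Section 11.4 does not say how sides are labelled or compared in these patients.

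**Working it through.** **1. The plan's own figure.** 0.20 × 250 = 50 hips, and 50 / 2 = 25 patients. The cap in section 9.2.2 reproduces. At the full quota there are 250 − 50 = 200 unilateral records and 50 bilateral ones, from 200 + 25 = 225 people.

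**2. Precision of an all-hips EQ-5D mean.** Let ρ be the correlation between the two records of one person. The documents give no value, so 0.5 to 1.0 is an assumption. With a common variance s²:

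Var(mean) = [200 + 25 × (2 + 2ρ)] s² / 250²

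An analysis that treats the records as independent uses s² / 250. The ratio of the two is the design effect, [200 + 25 × (2 + 2ρ)] / 250 = 1 + 0.2ρ.

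| ρ (assumed) | Design effect | Factor by which the SE is understated | Effective n (250 / design effect) |
|---|---|---|---|
| 0.5 | 1.10 | 1.05 | 227 |
| 0.8 | 1.16 | 1.08 | 216 |
| 1.0 | 1.20 | 1.10 | 208 |

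At ρ = 1 the interval has 1 / 1.095 = 0.91 of its proper width, about 9% too narrow.

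**3. Weighting.** Bilateral patients are 25 / 225 = 11.1% of people but 50 / 250 = 20% of records. An all-hips mean therefore differs from a per-person mean by (0.200 − 0.111) = 0.089 times the difference in mean EQ-5D between bilateral and unilateral patients. The documents do not give that difference.

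**4. Timing in staggered patients, from the order of the table columns.**
- Tables 6 and 8: the first hip's 1-year visit is drawn between the second hip's 6-week and 6-month visits.
- Table 9: it is drawn between the second hip's 3-month and 6-month visits.

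The EQ-5D is due at that 1-year visit in all three. As drawn, the first hip's 1-year value is taken within about six months of the second operation. Table 7 is not relied on here.

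**5. Gait.** No figure can be calculated, because the number of bilateral patients who are at UK sites and consent to gait analysis is not given. As drawn in Tables 6, 8 and 9, the first hip's 1-year and 5-year tests both follow the second operation. Section 9.4 also admits a contralateral hip arthroplasty that is at least six months old, except in patients having metal ion tests, for whom any other joint replacement is an exclusion.

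**The case against.** The strongest reply is that little depends on this. At most 25 people are involved and the endpoints are secondary. Revision, the primary endpoint, and both sample-size calculations are untouched. The protocol does not say that EQ-5D means will pool all hips as independent records, and an analysis plan could remove duplicates. All of this stands as a limit on size. It does not settle the matter, because the protocol's own schedule fixes what is collected and under which number.

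Several stronger readings are tempting and are not supported:

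- *The EQ-5D is duplicated in all 25 bilateral patients.* True duplication fits simultaneous patients. Staggered patients have separate visit columns for each hip, so their answers come from different dates and are related but not identical. The split between the two groups is not given, so 1.10 is a ceiling.
- *The gait data do not describe the hip they are recorded under.* Gait is measured for each side on two force plates, so each limb's parameters do describe that limb. Table 5 shows gait once per patient, not once per hip.
- *A planned side-to-side gait comparison is invalid.* No such contrast is stated as an endpoint or analysis. The wording in section 11.4 only labels the sides measured.
- *Twenty-five patients lack a gait comparator.* That assumes every bilateral patient is a consenting UK patient, whereas section 9.2.2 allows recruitment from all sites. Staggered patients also keep a non-operated side at any test before the second operation.
- *Older contralateral arthroplasties can occur throughout the trial.* The metal ion exclusion covers all of Cohort 1A and the first 14 patients of Cohort 1B.

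**Conclusion.** The EQ-5D point holds. Sections 9.2.1 and 9.2.2 and Table 5 ask for a hip-specific answer to an instrument that section 8.2.1 describes as general health. Simultaneous bilateral patients supply the same information twice. The first hip's later values in staggered patients are mixed with recovery from the other operation.

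The effect on precision is modest: an understated standard error by a factor of about 1.05 to 1.10. This assumes a full bilateral quota, a within-person correlation between 0.5 and 1.0, and an analysis that treats hips as independent. With fewer bilateral patients or a lower correlation it is smaller. No effect on a trial conclusion is shown.

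The gait point is a minor clarification. The label of a non-operated side fails for patients whose other hip is also replaced at that visit, while the measurements on each limb remain valid.

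**What to change.** **EQ-5D (section 9.2 and Tables 5 to 9).** Record it once per person per visit date. Link that answer to both hip records, with the time since each operation, and summarise it per person: 225 people at a full quota, not 250 hip records. Where a staggered patient has two dated answers near one reporting time point, fix in advance which one enters the per-person summary.

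Do not cut the data off at the second operation. If all 25 bilateral patients were staggered, that would remove the later general-health data behind up to 50 of the 250 hip records. Linking a dated answer to both hips deals with duplication and timing without that loss.

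**Gait (section 11.4).** State how sides are labelled when both hips are replaced. Limit any comparison with a non-operated side to patients whose contralateral hip is native at that visit, and report each limb's own parameters for everyone tested.

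**Cost.** An amendment to the bilateral sections and tables, and a link in the database between one person's two trial numbers. Simultaneous bilateral patients complete one fewer questionnaire per visit, so there are up to 25 fewer EQ-5D records per visit, all of them repeats of an answer already held. Any comparison with a non-operated side would have somewhat fewer patients.

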#### 9.2.2 Staggered Bilateral HRA

Patients who are enrolled into the study as part of Cohort 1A, Cohort 1B or 2 can undergo a HRA with a H1 implant on the contralateral side if they meet the inclusion/exclusion criteria, and pass the screening assessments. All staggered bilateral patients recruitment must be re-consented for the additional assessments before taking part in the study for their contralateral hip. At point of re-consent these patients will be registered again with the coordinating site for a unique identification number for their contralateral second hip.

Patients recruited in cohort 1A who opt to undergo HRA for the contralateral hip will follow the assessments as detailed in Table 6. Those patients in cohort 2 who opt to

undergo HRA for the contralateral hip will follow assessments as detailed in Table 7. Patients recruited in cohort 1B will follow the assessments as detailed in Table 8. These patients will undergo additional AP and Lateral radiographs and will be required to complete the following questionnaires for the contralateral second hip: Oxford Hip Score, EQ5D-5L, Harris Hip Score and Imperial Score (online only).

Bilateral and staggered bilateral patients can be recruited from all sites participating in the trial, however the total number of bilateral implants cannot exceed 20% of the total study sample size (250). Therefore only 25 patients (50 hips) can be recruited as a bilateral or staggered bilateral patient, once this number has been reached, recruitment for the contralateral hip will cease and recruitment will continue for uni-lateral hips only. Bilateral patients and those recruited for the contralateral hip as staggered bilateral patients will be registered as a separate patient for each hip with a unique trial identification number for both hips. Case Report Forms will be completed for each hip.

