# 10 Statistical Methods

## **10.1** Hypotheses and Sample Size

#### 10.1.1 Primary Objective - Safety and Efficacy Study

A total of 250 cases will be enrolled into the study at the 9 investigation sites.

When 250 cases are enrolled from all sites, enrolment will be stopped, regardless of the number contributed from each site.

The sample size is calculated based on the non-inferiority of the study device; the following hypotheses will be tested to test the difference in success rate (defined in section 2) of the study device with the reference rate with non-inferiority margin,  $\delta > 0$ :

$$H_0: \pi_0 - \pi \ge \delta$$
$$H_a: \pi_0 - \pi < \delta$$

Where  $\pi$  is success rate of study device and  $\pi_0$  is reference rate, respectively and  $\delta = 5\%$ . For these hypotheses, rejection of the null hypotheses will imply non-inferiority of the study device compared to the reference rate.

For the above hypotheses, the sample size for a specified  $\alpha$  and power  $(1 - \beta)$  is given by:

$$n = \frac{(z_a + z_b)^2 (\pi (1 - \mu))}{(\mu_0 - \mu - \delta)^2}$$

Where  $\delta$  is the non-inferiority margin and non-negative number [43].

The success rate for the study device is unknown for this population but there is no reason to believe that it would be less than reference rate of 93% (95%CI: 92.4-93.6%) [19]. Therefore, a conservative success rate of 93% of the study device is used at 10 years study.

The non-inferiority margin  $\delta$  of 0.05 is chosen in the study [43]. 225 subjects are required to achieve  $100(1 - \beta) \% = 80\%$  power to detect non-inferiority at the Significance level of  $\alpha = 0.05$  (single-sided hypothesis). Based on the experience, allowing 10% of the patients lost to follow up by the end of 10 years, a sample size of 250 cases are needed in this study. Therefore, 250 cases will be enrolled in the study (20 cases minimum to be recruited at each site; in case one centre is not able to recruit the allocated target size of cases, numbers can be picked up by the other centres).

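### Up to 50 of the 250 cases may be paired hips from 25 people, each registered as a separate patient, but the sample size assumes independent observations and makes no allowance for pairs

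*Protocol*

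**What the plan says.** Section 9.2.2 caps bilateral implants at 20% of 250 and spells this out: "Therefore only 25 patients (50 hips) can be recruited as a bilateral or staggered bilateral patient". Each such patient "will be registered as a separate patient for each hip with a unique trial identification number for both hips", and case report forms are completed per hip. Section 9.2.1 adds that simultaneous bilateral patients "will be required to complete the following questionnaires for the contralateral hip: Oxford Hip Score, EQ5D-5L, Harris Hip Score and Imperial Score"; Table 5 marks these, EQ-5D included, as separate assessments for both hips.

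Section 10.1.1 sets the primary sample size. The margin is 5 points against a 93% reference rate, and "a conservative success rate of 93% of the study device is used at 10 years study". It states that "225 subjects are required to achieve" 80% power at the 5% level ("single-sided hypothesis"). It then allows for 10% of patients lost and arrives at 250 cases. The unit thus moves from subjects to patients to cases within one paragraph.

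Section 10.2 names the non-inferiority test, 95% confidence intervals, a Kaplan-Meier estimate, log-rank and Cox methods, and t or Wilcoxon tests for pain and function. It does not mention two hips from one person.

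**The concern.** Two hips in one person share bone quality, activity level, death and loss to follow-up, and often the surgeon. If their revision outcomes are positively correlated, 50 paired hips carry less information than 50 unrelated hips. The sample size ignores this. The registration rule also gives the analyst a data set in which each record looks like a different patient. Section 9.6 builds the identifier from a site number and a chronological number. Section 12.3 leaves the key to identities with the investigator. The protocol does not require a person-level link in the analysis data.

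At stake is the precision claimed for the 10-year survivorship comparison. It is a single-arm comparison with a fixed literature rate, so its whole inference rests on the standard error of one estimate.

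**Working it through.** **Inputs.** From Section 10.1.1: reference and assumed success rate 0.93, margin 0.05 (null rate 0.88), one-sided alpha 0.05, power 0.80, 10% loss. From Section 9.2.2: at most 25 people with two hips among 250 cases. Assumption: rho is not in the protocol, so values of 0.1, 0.3, 0.5 and 1.0 are shown.

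**1. The plan's own figure.** With the variance at 0.88 under the null and 0.93 under the alternative:

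n = [1.645·√(0.88·0.12) + 0.842·√(0.93·0.07)]² / 0.05² = 224.6, so 225; and 225/0.9 = 250.

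Both figures reproduce, under independence. (Using the variance at 0.93 alone gives 161, so the power figures below use the version that yields 225.)

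**2. People behind the cases.** At the cap, 200 unilateral hips plus 25 people with two hips make 250 cases from 200 + 25 = 225 people. After 10% loss, 225 hips remain from 225·0.9 = 202.5, about 202 to 203 people.

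**3. Design effect.** Σm²/Σm = (200·1 + 25·4)/250 = 1.2, so DE = 1 + 0.2·rho. This assumes that the share of paired hips is the same after loss.

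**4. Two alternative consequences, for 225 evaluable hips.**

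- *Pairing ignored:* the true SE is √DE times the reported SE. True one-sided error = 1 − Φ(1.645/√DE). Power = Φ{[0.05 − 1.645·√(0.1056/225)] / √(DE·0.0651/225)}.
- *Pairing accounted for:* effective n = 225/DE; error stays at 5%. Power = Φ{[0.05 − 1.645·√(0.1056/n)] / √(0.0651/n)} at that n.

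| rho | DE | SE ratio | Ignored: true error | Ignored: power | Accounted for: effective n | Accounted for: power |
|---|---|---|---|---|---|---|
| 0 | 1.00 | 1.000 | 5.0% | 80.1% | 225 | 80.1% |
| 0.1 | 1.02 | 1.010 | 5.2% | 79.8% | 221 | 79.3% |
| 0.3 | 1.06 | 1.030 | 5.5% | 79.4% | 212 | 77.6% |
| 0.5 | 1.10 | 1.049 | 5.8% | 79.0% | 205 | 76.0% |
| 1.0 | 1.20 | 1.095 | 6.7% | 78.0% | 188 | 72.2% |

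The 95% half-width at 93% and 225 hips is 1.96·√(0.0651/225) = 3.33 points. Multiplied by the SE ratio it becomes 3.37, 3.43, 3.50 and 3.65 points.

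**5. Below the cap.** With 10 bilateral patients, Σm²/Σm = (230 + 40)/250 = 1.08, so DE = 1 + 0.08·rho. Even rho = 1 then gives an SE ratio of √1.08 = 1.04.

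**The case against.** The strongest reply is that the registration rule governs identifiers and forms, not analysis. Section 10.2 does not say that hips will be treated as independent, and a clustered variance is something a statistical analysis plan may well specify. The endpoint in Section 8.1.3 is revision of the prosthesis, so the hip is a natural unit. The 20% cap, which Section 11.2.2 has checked at each bilateral consent, already limits the damage. The coordinating site re-registers the second hip, so the pairing is probably recoverable.

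Much of this stands. It rules out four stronger readings that a reader might draw:

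- *That the primary interval is too narrow.* This needs both a positive correlation and an analysis that ignores pairing; the protocol establishes neither. Nor does Section 10.2 say which bound decides. If it were the lower limit of a two-sided 95% interval, the unadjusted error at rho = 1 would be 1 − Φ(1.96/1.095) = 3.7%, below 5%.
- *That inflated error and the larger loss of power occur together.* They belong to different analyses. Power near 72% is the result of a correct analysis at perfect correlation, not of ignoring the pairs.
- *That second hips tilt the result upward because patients return only after a good first hip.* Section 9.2.2 does let patients opt for a second H1, and Section 9.4 excludes a contralateral hip arthroplasty in the preceding 6 months. Selection is therefore possible for staggered cases. Nothing states it or sizes it, and it does not apply to simultaneous cases.
- *That EQ-5D will be analysed twice per person.* The protocol fixes double collection, not double analysis. For staggered patients the schedules place the two hips' assessments at different times.

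The reply does not answer the sample size. Its basis, its shifting unit and the absence of any allowance for the permitted pairs are fixed in Sections 9.2.2 and 10.1.1. An analysis plan can adjust the variance, but that does not restore the stated 80%.

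**Conclusion.** The point holds in a bounded, conditional form. The calculation gives 80.1% power under independence, so at the cap a correlation of 0.1 or more puts a properly adjusted test below the stated 80%: by about 1 to 4 points for rho 0.1 to 0.5, and by about 8 points at the extreme. If the pairs are ignored instead, the true standard error is 1% to 5% above the reported one over that range, and at most 9.5%.

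The 225 subjects are still 225 people at enrolment; the shortfall, to about 202 or 203 people, appears only after loss to follow-up. These sizes rest on an assumed rho, on the cap being reached, and on the variance form that reproduces 225. This is a modest defect worth correcting. It does not invalidate the design.

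**What to change.** - Record a person-level identifier that links the two hip identifiers, and do so now. Rebuilding the link from site records after ten years would be harder.
- State that the hip is the unit of analysis, and use one term in place of subject, patient and case in Sections 10.1.1 and 10.2.
- Use a patient-clustered variance (robust or bootstrap) for the 10-year Kaplan-Meier and non-inferiority interval, and for the Cox and patient-reported outcome analyses.
- Add a sensitivity analysis with the first implanted hip per person (one hip for simultaneous cases). It would also show any selection of second hips.
- Analyse EQ-5D once per person per time point for simultaneous bilateral cases, and with clustering for staggered ones.
- Restate effective size and power at the 20% cap over a stated range of rho, as in the table above, without enrolling more patients.

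The cost is one linking variable, some analysis wording, slightly wider intervals and a slightly lower stated power.
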